## 8. SELECTION AND WITHDRAWAL OF SUBJECTS

Subjects must meet all of the inclusion criteria and none of the exclusion criteria to be eligible to participate in the study.

### 8.1. Subject Inclusion Criteria

1. Male and female subjects age  $\geq$  18 years.
2. The subject must meet one of the following two criteria:
  - a. A positive influenza Rapid Antigen Test (RAT) and/or a FDA-approved PCR test and at least one clinical sign or symptom consistent with acute influenza infection as listed in 2b below.

**OR**

- b. Clinical signs and symptoms consistent with acute influenza infection consisting of an oral temperature  $\geq$  100°F (37.8°C) with at least one respiratory symptom of at least moderate severity (cough or rhinitis) and at least one constitutional symptom of at least moderate severity (myalgia [aches and pains], headache, feverishness, or fatigue). **Note: Enrollment at each site by clinical symptoms alone will be approved by the Sponsor at the beginning of each influenza season once influenza has been confirmed in the local community. The Sponsor may withdraw approval for symptomatic screening in any season based upon trends in influenza surveillance data. Prior to Sponsor approval or after approval is withdrawn, Criteria 2 must be met by a positive influenza RAT test and/or PCR. During the period of approval, clinical symptoms alone will be adequate to meet Criteria 2.**
3. Onset of symptoms no more than 48 hours before presentation for screening. However, due to historically delayed presentation for medical care in the adult population, approximately 20% of the elderly population may be enrolled with symptoms starting  $>$  48-hours but  $\leq$  72-hours prior to presentation for screening. Note: Time of onset of illness is defined as either (1) the time when the temperature (either oral or rectal) was first measured as elevated (at least one °C of elevated temperature), OR (2) the time when the subject experienced the presence of at least one respiratory symptom AND the presence of at least one constitutional symptom together.
4. Either age  $\geq$  65 years AND/ OR presence of one of the following risk factors:
  - a. Pregnancy, including women who are up to 2 weeks postpartum
  - b. Resident of a nursing home or long-term care facility
  - c. History of chronic lung disease including obstructive pulmonary disease (COPD), persistent asthma or cystic fibrosis
  - d. History of heart disease including myocardial infarction, angina requiring treatment, congestive heart failure requiring treatment, arrhythmia including atrial fibrillation and valvular dysfunction
  - e. History of blood dyscracias including sickle cell anemia and thalassemia
  - f. History of renal impairment (creatinine clearance [CrCl]  $<$  50 mL/min as determined by the Cockcroft-Gault formula) ([Cockcroft and Gault 1976](#)), including dialysis.

- g. History of liver disease including cirrhosis
  - h. Mild to moderate immunocompromise, including: history of HIV disease on stable HAART with last known CD4+ count  $\geq 200$  cells/ $\mu$ L; known neutropenia with ANC  $> 500$  cells/ $\mu$ L; chronic corticosteroid use of  $< 20$  mg/d for any indication.
  - i. History of diabetes mellitus
  - j. Morbid obesity (body mass index [BMI]  $\geq 40$ )
  - k. American Indian or Alaskan native
5. Written informed consent

## 8.2. Subject Exclusion Criteria

1. Subjects who in the opinion of the investigator require hospital admission to treat medical condition(s) which, in the Investigator's opinion, could represent complications of influenza. Note, hospitalization is not an exclusion criterion when it is the usual practice of the treating institution to hospitalize elderly patients with acute uncomplicated influenza.
2. Women who plan to breast-feed for the first 48 hours after study drug administration. However, women who suspend breast feeding for 48 hours after study administration may participate.
3. Employees of the study site, or immediate family members of study site employees
4. Presence of clinically significant signs of acute respiratory distress.
5. Clinical evidence of worsening of any chronic medical condition (temporally associated with the onset of symptoms of influenza) which, in the Investigator's opinion, indicates that such finding(s) could represent complications of influenza
6. Current clinical evidence, including clinical signs and/or symptoms consistent with a bacterial infection, including: otitis media, bronchitis, sinusitis and/or pneumonia, or active bacterial infection of any body site that requires therapy with oral or systemic antibiotics
7. Immunization against influenza with live attenuated virus vaccine (FluMist®) in the previous 14 days
8. History of alcohol abuse or drug addiction within 1 year prior to admission in the study
9. Participation in a study of any investigational drug or device within the last 30 days
10. Previous participation in study BCX1812-305 (pediatric study) or BCX1812-306 (this study)
11. Presence of any pre-existing illness that, in the opinion of the Investigator, would place the subject at an unreasonably increased risk through participation in this study or would make the subject unable to comply with the protocol.

### **8.3. Withdrawal Criteria**

Participation in the study is strictly voluntary. Subjects have the right to withdraw from the study at any time and for any reason. A subject's participation will be terminated:

- At the subject's request
- If, in the Investigator's or Sponsor's opinion, continuation in the study would be detrimental to the subject's well-being
- If the subject is not able to comply with the study requirements
- If the Sponsor terminates the study
- If a regulatory authority requires that all study activities be halted

In all cases, the reason for withdrawal must be recorded in the subject's medical records (source documents). If the reason for subject withdrawal is not known, the subject must be followed to establish whether the reason was an AE, and if so, this must be reported in accordance with the procedures outlined in Section 11.1.2. Vigorous attempts should be made for follow-up of all subjects who miss a study visit. In general, subjects will be encouraged to complete the scheduled procedures. The subject will require an Early Withdrawal Visit if withdrawn from the study prior to scheduled study completion.

To the extent possible, all scheduled end-of-study assessments (including the Early Withdrawal Visit) should be performed on all participating subjects who withdraw from the study before the Day 14 Visit.

Subjects withdrawn from the study at any time other than during the screening period will not be replaced.

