## 10. STUDY CONDUCT

### 10.1. Overview

Approximately 120 subjects will be enrolled in this open-label study (a minimum of 80 elderly subjects [ $\geq 65$  years] will be enrolled). A subject's duration of participation in this study is expected to be 14 days and will include up to 4 clinic visits. It is expected that most subjects will have the Screening visit and the Day 1 Treatment visit on the same day. Subjects will be discharged from this study on Day 14.

Additional, unscheduled visits may be required for subjects who report symptoms of influenza of moderate or severe intensity at Day 14 or have persistent adverse events and/or treatment-emergent laboratory findings that require medical monitoring or management.

All subjects will receive a single dose of IV peramivir (600 mg or reduced for renal impairment). Subjects will undergo follow-up clinical assessments on Days 3, 7, and 14.

An adequate nasal swab specimen will be collected from all enrolled subjects at Baseline (pre-dose) for virus subtype identification and quantitative virologic assessments and at the follow-up assessments on study Days 3, 7 and 14.

Specimens from all subjects yielding influenza virus will also be assessed for susceptibility to neuraminidase inhibitors (Day 1 and last specimen yielding influenza virus on culture). A central laboratory will perform all virologic assessments.

Up to 3 blood samples will be drawn to obtain plasma samples for drug concentration determinations, where possible, during the following time periods, beginning from the end of dosing until release from the site:

- One time point immediately following completion of the infusion
- One time point from 30 minutes to 1 hour post-infusion
- One time point from 1 hour to 3 hours post-infusion

Adverse events and concomitant medications will be monitored at each scheduled visit from the Screening assessment to final study visit. Clinical laboratory investigations (chemistries, hematology, and urinalysis) will be collected at Baseline, Day 7 and Day 14 visits. Safety and tolerability will be evaluated through assessments of AEs, laboratory analyses (clinical chemistry, hematology, and urinalysis), vital signs and physical examinations at the time points indicated in the schedule of assessments.

All subjects/caregivers will record the following information in a Subject Diary:

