### Adverse Events

Adverse events will be assessed and recorded at the indicated time points (see schedule of assessments, [Table 1](#)). AEs will be recorded on Screening, Day 1, Day 3, Day 7 and Day 14/Early Withdraw visits. Adverse events will be graded through use of the Division of Acquired Immune Deficiency Syndrome (DAIDS) Tables for Grading Adult and Pediatric Adverse Experiences (see [Appendix 16.2](#)). Any Grade 3 and Grade 4 clinical AEs or laboratory abnormalities that are judged to be possibly, probably, or definitely related to study treatment will be promptly (within 72 hours) reported to the study medical monitor unless the event meets criteria for an SAE, in which case they must be reported within 24 hours. Influenza-related complications are not considered AEs unless they meet the criteria for SAEs. Full details on recording and reporting AEs are provided in [Section 11.1.2](#).

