#### **11.1.2. Method, Frequency, and Time Period for Detecting Adverse Events and Reporting Serious Adverse Events**

Reports of AEs are to be collected from the time the subject signs the informed consent through the follow-up period ending on Day 14. The Investigator or designee must completely and promptly record each AE. The Investigator should attempt, if possible, to establish a diagnosis based on the presenting signs and symptoms. In such cases, the diagnosis should be documented as the AE and not the individual sign/symptom. If a clear diagnosis cannot be established, each sign and symptom must be recorded individually. If a final diagnosis is established during evaluation or treatment, the source documents will be updated accordingly.

The Investigator should attempt to follow all unresolved AEs and/or SAEs observed during the study until they are resolved, or are judged medically stable, or are otherwise medically explained.

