4.3. SAFETY POPULATION

The safety population will include all enrolled subjects who receive any amount of study drug. The safety population will be the primary population for all analyses of safety data.

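### After a dosed subject is withdrawn, no procedure detects new adverse events up to Day 14, and the SAP then counts that unobserved time as event-free

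*Protocol*

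**What the plan says.** Protocol Section 8.3 introduces its list with "A subject's participation will be terminated". One condition on the list is "If the subject is not able to comply with the study requirements". The wording is mandatory and makes no distinction between before and after dosing. Section 10.1 gives each subject one infusion, on Day 1.

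The same section contains safeguards. "The subject will require an Early Withdrawal Visit if withdrawn from the study prior to scheduled study completion". Sites are to pursue subjects who miss a visit, encourage completion, carry out end-of-study assessments where possible, and find out whether an unexplained withdrawal was due to an AE. Section 11, under Adverse Events, adds: "AEs will be recorded on Screening, Day 1, Day 3, Day 7 and Day 14/Early Withdraw visits".

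Section 11.1.2 sets the AE window from consent to Day 14. It says the investigator "should attempt to follow all unresolved AEs and/or SAEs observed during the study until they are resolved", or are stable or otherwise explained. Section 10.1.2.5 places the final procedures, including the AE review, at Day 14 or at the time of early withdrawal.

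On the analysis side, SAP Section 4.3 reads: "The safety population will include all enrolled subjects who receive any amount of study drug". SAP 3.3.8 defines a treatment-emergent event as one reported on the CRF within 14 days of the dose. SAP 3.3.4 rules out imputation beyond its listed conventions, and SAP 5.3.1 summarizes numbers of subjects with events. SAP 5.1 summarizes days on study, under disposition.

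**The concern.** Safety is the primary endpoint (Protocol 7.1.1), and the trial is a 14-day observation after one infusion. Once the infusion is complete, ending participation cannot undo exposure. What it ends is visits, sampling and observation. If observation ends early in some treated subjects while they still count in full in the denominator, the reported incidence is too low.

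The loss may also be related to risk. At least 80 of about 120 subjects are to be 65 or older, and nursing-home residents are eligible. Exclusion 11 already removes people whose pre-existing illness would stop them complying. Inability that arises after the dose may therefore reflect new deterioration. That is a plausible inference; the documents do not state it. The same gap reaches two secondary endpoints, influenza-related complications and hospital admission.

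**Working it through.** **Step 1: what covers the period from withdrawal to Day 14?**

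| Provision | Events up to last contact | New events from last contact to Day 14 |
|---|---|---|
| Early Withdrawal Visit (8.3, 11) | recorded | not covered; the visit replaces Day 14 (10.1.2.5) |
| Follow-up of unresolved events (11.1.2) | followed to outcome | only events already observed |
| Pursuit of missed visits, inquiry into unknown reason (8.3) | yes | no contact specified once the subject is withdrawn |
| AE window to Day 14 (11.1.2, Table 1 footnote 9) | yes | nominally open, with no procedure |
| Serious AE reporting (11.1.5) | yes | depends on the investigator becoming aware |

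The gap is confined to new events after the last contact.

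**Step 2: what does the SAP do with that period?** The denominator is all treated subjects, the numerator is reported events, and there is no imputation and no person-time rate. An unreported event after last contact counts as no event.

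**Step 3: illustrative size.** The documents state no withdrawal rate and no figure to reproduce. The inputs below, apart from the 14-day window, are assumptions:

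- d, the share of treated subjects withdrawn: 3%, 5% or 10% (3.6, 6 or 12 of 120)
- withdrawal around Day 5, so 9 of the 14 days are lost
- constant risk over the 14 days
- r, the risk in those withdrawn relative to the rest: 1 or 3

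Share of events unobserved = d × r × (9/14) / [(1 − d) + d × r]

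| d | r = 1 | r = 3 |
|---|---|---|
| 3% | 0.03 × 0.643 = 1.9% | 0.09 × 0.643 / 1.06 = 5.5% |
| 5% | 0.05 × 0.643 = 3.2% | 0.15 × 0.643 / 1.10 = 8.8% |
| 10% | 0.10 × 0.643 = 6.4% | 0.30 × 0.643 / 1.20 = 16.1% |

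For a sense of scale, take an assumed true incidence of 20%. At d = 5% it would be reported as 20% × (1 − 0.032) = 19.4% at equal risk, and 20% × (1 − 0.088) = 18.2% at threefold risk. At d = 10% the figures are 18.7% and 16.8%.

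**Step 4: events never seen.** The one-sided 95% upper bound for zero events in n subjects is 1 − 0.05^(1/n). With all 120 followed it is 2.47%. If 10% contributed nothing usable (n = 108) it is 2.74%. For 80 elderly subjects the figures are 3.68% and, at n = 72, 4.08%. This is an extreme case, because withdrawn subjects do contribute their time up to last contact.

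**The case against.** The strongest reply is that the documents are silent here and do not order collection to stop. The AE window runs to Day 14 with no exception for withdrawn subjects, and Section 8.3 itself holds several safeguards. An all-treated denominator is conventional, the analysis is descriptive, and SAP 5.1 already reports completion, discontinuation reasons and days on study.

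Much of this stands, and it rules out several stronger readings that a reader might infer:

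- *AE collection stops at withdrawal, and these subjects count as event-free.* No sentence says collection stops. Events up to the Early Withdrawal Visit are recorded and counted.
- *Missing a diary entry or visit leads to removal.* The criterion concerns inability to comply. Missed visits trigger pursuit (8.3), and missed diary entries trigger a reminder (10.2.2).
- *Ending participation protects no one.* It spares a frail subject visits, blood draws and nasal swabs.
- *Subjects admitted to hospital are lost.* Section 10.2.5 asks for additional information on any admission during the study.
- *With 5% withdrawn, six events could go unseen.* That requires all 6 to have a new event after leaving. At the highest 600 mg rate in Section 5.3.1.2 (7.6%), the expected number missed for that event is 6 × 0.076 × 9/14 = 0.3, or 0.9 at threefold risk.

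The reply does not supply a procedure for the interval after withdrawal. A window with no contact behind it finds only events that happen to be volunteered. Days on study in a disposition table also do not tell a reader of the AE tables how many subjects were observed to Day 14.

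**Conclusion.** The point holds as a gap in follow-up and reporting. Section 8.3 requires participation to end for dosed subjects who cannot comply, nothing implements the Day 14 window for new events after that, and the SAP makes no allowance for the shorter observation. Any bias from this is downward.

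Under the stated assumptions, roughly 2% to 6% of events would be missed at equal risk and 5% to 16% at threefold risk. These figures are illustrative. They rest on an assumed withdrawal rate, an assumed departure around Day 5 and constant risk. If events cluster soon after the infusion, the loss is smaller. If few subjects leave and leaving is unrelated to outcome, it is negligible. The change is worth making because safety is the primary endpoint, withdrawn subjects are not replaced, and the remedy is cheap.

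**What to change.** **Protocol 8.3.** State that, for subjects who have received study drug, inability to comply or stopping visits ends only the procedures that cannot be done. AE, serious AE and hospital-admission information continues to be collected to Day 14, by telephone or from records, unless the subject withdraws consent for follow-up. The compliance criterion itself need not be deleted.

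**SAP safety tables.** Report, by age group, the number of safety-population subjects with AE ascertainment to Day 14.

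**Cost.** A few sentences in 8.3, one line in the SAP, and a few calls by existing site staff. The downside is some partially complete records in the database.

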**Table 1. BCX1812-306: Schedule of Assessments**

Assessments	Screening 	Baseline  (Pre-dose)	Day 1 Treatment Day 	Day 3	Day 7 (+ 2 days)	Day 14 (+ 3 days) / End of Study	Early Withdrawal
Informed Consent	X						
Inclusion/Exclusion Criteria	X						
Medical History/Physical Exam	X			X 	X 		
Vital Signs 	X			X	X	X	X
Body Temperature 	X	X	X	X	X	X	X
Clinical Chemistries and Hematology 		X			X		X
Urinalysis 		X			X		X
Pregnancy Test (Urine or Serum)	X					X	X
Assessment of influenza symptoms 	X		X	X	X	X	X
Ability to Perform Usual Daily Activities 		X		X	X	X	X
Influenza Related Complications (IRC) 	X			X 	X	X	X
Concomitant Medications Review	X		X	X	X	X	X
Subject Diary Review			X	X	X	X	X
Pharmacokinetic (PK) Sampling			X				
Serum sample for influenza antibody analysis 		X		X	X		X
Swabs for Virology Analysis		X		X	X		X
Rapid antigen test (RAT) or FDA- approved PCR test for influenza A and B on nasal specimen	X						

Assessments	Screening	Baseline (Pre-dose)	Day 1 Treatment Day	Day 3	Day 7 (+ 2 days)	Day 14 (+ 3 days) / End of Study	Early Withdrawal
Study Drug Administration			X				
Adverse Events 	X	X	X	X	X	X	X

- 1 It is expected that the date of Screening, Baseline, and Day 1 (date of study drug administration) will be the same. Day 1 consists of pre and post-dose assessments.
- 2 Vital sign measures will include blood pressure, pulse rate, and respiration rate. Vital signs will be recorded once during Screening, and vital signs will be taken once on remaining study visit days.
- 3 The investigator will record oral body temperature at Screening. Thereafter, the subject or care giver will record oral body temperature approximately every 12 hours in the Subject Diary until temperature normalizes for 48 hours (i.e. temperature without antipyretic is < 37.4°C/ 99.4°F orally for 4 measurements).
- 4 Clinical laboratory assessments performed at Screening are for the purpose of establishing a baseline. Subjects may be enrolled and begin treatment with study drug prior to receiving results. These labs may be done at any visit if necessary for patient management or adverse event monitoring purposes.

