#### **10.1.2.5. Day 14 (End of Study)**

The Day 14 assessments will be performed as a clinic visit. The following procedures/assessments will be performed on Day 14 (+ 3 days) or at the time of early withdrawal, where possible:

- Measure vital signs (blood pressure, pulse rate, and respiration rate)
- Measure and record oral body temperature
- Perform a urine or serum pregnancy test (non-pregnant females of childbearing potential only)
- Conduct an assessment for the presence of possible IRC; if an IRC is suspected, a targeted physical exam should be conducted to confirm the absence or presence of the IRC
- Review the subject diary for completeness
- Collect a bilateral adequate nasal swab specimen for viral culture, quantitative PCR assay and susceptibility to neuraminidase inhibitors.
- Review and record concomitant medications
- If Day 7 labs are, in the opinion of the investigator, significantly abnormal or significantly changed from baseline, collect blood specimen for clinical chemistry and/or clinical hematology tests as specified in Sections [11.2.1](#) and [11.2.2](#) and a serum sample for future influenza antibody analysis.
- If Day 7 urinalysis is, in the opinion of the investigator, significantly abnormal or significantly changed from baseline, collect urine for urinalysis
- Review and record AEs

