### **11.2. Clinical Laboratory Evaluations**

#### **11.2.1. Clinical Chemistry Profiles**

Clinical chemistry profiles will include a Chemistry 20 panel (includes sodium, potassium, chloride, total CO2 [bicarbonate], creatinine, glucose, urea nitrogen, albumin, total calcium, total magnesium, phosphorus, alkaline phosphatase, alanine aminotransferase (ALT), aspartate aminotransferase (AST), total bilirubin, direct bilirubin, lactate dehydrogenase (LDH), total protein, total creatine kinase, and uric acid).

Blood samples for clinical chemistry profiles will be collected at Screening and at Day 7 or early termination visit (if the early termination visit occurs prior to Day 7). Clinically significant results should be reported as AEs. If Day 7 clinical chemistry profiles are, in the opinion of the investigator, significantly abnormal or significantly changed from baseline at Day 7, they should be repeated at the Day 14 visit.

At screening, creatinine clearance will be calculated by the Cockcroft-Gault equation (using actual body weight and serum creatinine) (see Appendix 16.1).

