### **11.4. Physical Examination**

The Investigator will perform a full physical examination at Screening, including the subject's height and weight, and a targeted physical examination on Day 3 and Day 7 and/or early termination. Examination of the breast and urogenital system may be omitted as per the institution's/investigator's clinical routine. At each follow-up visit, study personnel will evaluate the subject for the presence of clinical signs and/or symptoms of influenza-related complications (see Section 10.2.4). If an IRC is suspected, a targeted physical exam should be conducted to confirm the absence or presence of the IRC.

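### The passages that set the content of the Early Withdrawal visit conflict on safety laboratory tests and the exit examination, and the SAP shift tables leave out Early Withdrawal results

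*Protocol*

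**What the plan says.** **The visit.** Protocol 8.3 makes the visit mandatory: "The subject will require an Early Withdrawal Visit if withdrawn from the study prior to scheduled study completion". It adds: "To the extent possible, all scheduled end-of-study assessments (including the Early Withdrawal Visit) should be performed on all participating subjects" who leave before Day 14. It gives no itemised content.

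**Laboratory tests.** Table 1 and the matching schedule in SAP 1.2 mark chemistry, hematology and urinalysis in the Early Withdrawal column without condition, and SAP 1.1 says the same in prose. Protocol 11.2.1 takes chemistry samples "at Day 7 or early termination visit (if the early termination visit occurs prior to Day 7"), and 11.2.2 and 11.2.3 carry the same rule for hematology and urine. Section 10.1.2.5 opens: "The following procedures/assessments will be performed on Day 14 (+ 3 days) or at the time of early withdrawal, where possible". Its blood item reads "If Day 7 labs are, in the opinion of the investigator, significantly abnormal or significantly changed from baseline, collect blood specimen", and its urine item carries the same kind of condition on the Day 7 urinalysis.

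**Examination.** Protocol 11.4 provides for "a targeted physical examination on Day 3 and Day 7 and/or early termination". In Table 1 and SAP 1.2, the row "Medical History/Physical Exam" is marked at Screening, Day 3 and Day 7 and is blank at Early Withdrawal; footnote 6 names Days 3 and 7 only. Section 10.1.2.5 asks for an examination only when an influenza-related complication is suspected.

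**Analysis.** Protocol 13.9 plans toxicity shifts from baseline to post-baseline values. SAP 5.3.3 and the titles of its three shift tables (chemistry, hematology, urinalysis) restrict the shift to Day 7, and SAP 3.3.6 assigns results by nominal visit.

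**The concern.** Laboratory abnormalities and physical examinations are named components of the primary safety endpoint (Protocol 7.1.1). Day 7 is the first scheduled post-dose laboratory visit. If the Early Withdrawal sample is not drawn from a subject who leaves before Day 7, no scheduled post-dose laboratory value exists for that subject. Withdrawn subjects are not replaced, so the value cannot be recovered.

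Section 10.1.2.5 is the only itemised visit list in Section 10 that says it covers early withdrawal, so study staff could reasonably work from it. A list whose laboratory items can never be triggered for some of the subjects it covers is a drafting fault, whatever other sections say. The SAP adds a separate gap: even when the sample is drawn as Table 1 directs, the shift tables have no place for it.

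**Working it through.** The documents give no figure to reproduce. The check sets the passages side by side for a subject who leaves after dosing but before Day 7.

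| Source | Chemistry, hematology, urinalysis | Physical examination |
|---|---|---|
| Protocol Table 1; SAP 1.2 | Yes, no condition | Not marked |
| SAP 1.1 | Yes | Not itemised by visit |
| Protocol 11.2.1 to 11.2.3 | Yes, when before Day 7 | Not covered |
| Protocol 11.4 | Not covered | Targeted examination named |
| Protocol 10.1.2.5 | Only after a notable Day 7 result | Only if a complication is suspected |

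**Step 1, laboratory tests.** The trigger in 10.1.2.5 needs a Day 7 result. This subject has none, so the trigger cannot fire. Used alone, 10.1.2.5 yields no scheduled post-dose laboratory value; Table 1 or 11.2 yields one. For a subject who leaves after Day 7 with a result in hand, the condition in 10.1.2.5 does work, and it agrees with 11.2. The unmeetable case is confined to subjects without a Day 7 result.

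**Step 2, examination.** Section 11.4 names one at early termination, the two schedules do not mark it, and 10.1.2.5 makes it conditional. The sources are more evenly split here. The and/or in 11.4 also makes its instruction less than categorical.

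**Step 3, analysis.** An Early Withdrawal sample does not carry the nominal visit Day 7, so under SAP 3.3.6 and 5.3.3 it does not enter the shift tables. SAP 5.4 lets the SAP override the protocol, so the narrower rule would govern. SAP Section 6 does not list the narrowing among its changes. The same sample does enter the treatment-emergent toxicity summary, because SAP 3.3.8 counts a grade increase at any post-baseline visit up to 14 days after dosing. It also appears in the listings.

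**Step 4, scale.** The documents do not say how many subjects leave before Day 7. As an assumption, take 2%, 5% or 10% and suppose that every one of them goes unsampled. The one-sided 95% upper bound on an event rate when no events are seen in n subjects is 1 − 0.05^(1/n).

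| Assumed loss | Of 120: lost, n left, bound | Of 80 elderly: lost, n left, bound |
|---|---|---|
| None | 0, 120, 2.47% | 0, 80, 3.68% |
| 2% | 2, 118, 2.51% | 2, 78, 3.77% |
| 5% | 6, 114, 2.59% | 4, 76, 3.87% |
| 10% | 12, 108, 2.74% | 8, 72, 4.08% |

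Even the 10% row moves the bound by only 0.27 percentage points overall (2.74 − 2.47) and 0.40 in the elderly (4.08 − 3.68).

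**The case against.** The strongest reply is that the documents already settle the laboratory question. Table 1, three subsections of 11.2 and two SAP sections require the samples, and 11.2 covers the very case of leaving before Day 7. Section 8.3 itself points to the Early Withdrawal Visit, which is a named column in Table 1 with the laboratory rows marked. The blood item in 10.1.2.5 refers the reader to 11.2.1 and 11.2.2, where the early-termination rule stands. Footnote 4 of Table 1 also permits laboratory tests at any visit for subject management or adverse event monitoring. Most of this stands. The samples are lost only where a site works from 10.1.2.5 alone, and the footnote permits tests without requiring them. None of it makes the 10.1.2.5 condition workable.

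A reader might infer four stronger conclusions that the documents do not support:

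- **That the plan takes no laboratory tests from early leavers.** Most of the passages say the opposite.
- **That an early leaver has no post-dose examination.** A subject seen on Day 3 has had a targeted one; what may be missing is the exit examination. SAP 5.3.4 only lists examination findings, so the analytic effect is small.
- **That an Early Withdrawal result is lost to the safety analysis.** It is absent only from the shift tables.
- **That early leavers are mainly subjects with safety problems.** Treatment is a single infusion, so leaving is not the same as stopping drug. Section 8.3 lists reasons unrelated to safety and requires follow-up when the reason is unknown, to establish whether it was an adverse event. Selective loss is possible, but nothing in the documents shows it.

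**Conclusion.** The contradiction is real and minor. Section 10.1.2.5 sets a laboratory condition that a subject leaving before Day 7 can never meet, against several passages that require the tests. The exit examination is named in one section, unmarked in both schedules and conditional in a third place. The SAP narrows the shift analysis planned in Protocol 13.9 to Day 7 without recording the change.

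The number of subjects affected is not given and is probably small. Under the assumed 2% to 10% loss, with every such subject unsampled, the effect on precision is slight. The reason to act is that the correction is almost free and protects a component of the primary safety endpoint.

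**What to change.** - **Laboratory tests.** Reconcile 10.1.2.5 with Table 1, 11.2.1 to 11.2.3 and SAP 1.1 and 1.2, so that the Day 7 condition applies only to subjects who have a Day 7 result.
- **Examination.** Reconcile 11.4, Table 1 with its footnote 6, SAP 1.2 and 10.1.2.5 so that all say the same about an exit examination. This review does not say which is right.
- **Shift tables.** In SAP 5.3.3, use the Early Withdrawal result as the post-baseline value when there is no Day 7 result, in line with Protocol 13.9. Adjust the titles of the three shift tables to match.

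The cost is some wording, possibly one cell in each schedule, and one derivation. The laboratory change adds no test beyond those already in Table 1 and 11.2. Whether the examination is an added procedure depends on how that conflict is settled. The drawback is that post-baseline values in the shift tables would no longer all come from Day 7, which a footnote should state.
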